# **1. STUDY RATIONALE**

## ***1.1. LYMPHOMA***

Lymphomas are malignant hemopathies of lymphoid tissue, of ganglionic or extranodal origin. A classic distinction is made between Hodgkin's disease (MDH) and Non-Hodgkin's lymphomas (NHL).

Lymphoma is the 6th cancer in terms of incidence in France, where around 11,000 new cases are diagnosed each year. Most types of lymphoma are found at all ages with a predominance in the elderly.

The most common diagnostic circumstance is detection of malignant lymphoma in the form of a lymph node mass. When these lymphadenopathies are deep and voluminous, they can be revealed by the presence of various and non-specific symptoms: cough, pleural pain, vena cava depressive syndrome, abdominal pain, transit disorders, etc.

Since these tumors are highly chemo-sensitive, treatment is mainly based on chemotherapy: chemo-immunotherapy for NHL and radio-chemotherapy for Hodgkin's lymphoma.

For "aggressive" lymphomas, current chemotherapy regimens achieve a complete remission rate of 60 to 80% (1) and a 5-year survival rate of approximately 70%.

Thanks to the continuous improvement of diagnostic techniques and treatments, the prognosis of lymphomas is constantly improving. However, 20 to 40% of patients most often relapse within 2 or 3 years after the end of treatment (2, 3).

In the event of a relapse, the treatment regimen usually offered to patients consists of salvage chemotherapy followed by an autologous transplant.

## ***1.2. PATIENT FOLLOW-UP***

The objectives of post-treatment follow-up are to:

- detect local or remote recurrences,
- detect and manage late complications related to treatment as well as sequelae,
- organize the necessary supportive care,
- ensure the quality of life
- early detection of a second cancer.

The current monitoring framework includes a clinical examination and a biological assessment every 3 months for 2 years and then every 6 months up to 5 years and an imaging assessment every 6 months. However, the value of this systematic imaging surveillance is controversial (4-7) and no randomized study has been carried out on this subject. Several observational studies suggest that systematic imaging surveillance can detect patients with asymptomatic relapse, but none show earlier relapse detection (8, 9), nor any difference in survival.

According to Voss et al for patients (children or adolescents) followed for Hodgkin lymphoma in remission, the majority of relapses were detected by the appearance of symptoms, clinical manifestations or laboratory abnormalities (4, 10-13).

Another problem is the repeated exposure to radiation during each scan with a potentially increased risk of a second cancer (15, 16). These imaging tests can also generate anxiety in patients in asymptomatic remission, especially just before and while awaiting the results of these tests. Imaging

CONFIDENTIAL

assessment can lead to the detection of false positives, which involves performing additional examinations, including biopsies that are also painful, expensive and anxiety-inducing (14).

These constraints would be acceptable if the relapse was detected before clinical manifestations and allowed patient survival to be increased.

Thompson et al recently published the results of a study regarding the utility of imaging surveillance in a large cohort study in patients with diffuse large B-cell lymphoma. Routine imaging surveillance allows detection of asymptomatic relapse in only 1.7% of patients (17, 18).

In this context, Huntington et al assessed the medico-economic impact of routine imaging surveillance. The results show that the clinical benefit of systematic imaging monitoring of asymptomatic patients in remission is very low or even zero compared to the substantial cost incurred (19).

### **1.3. MOOVECARE TOOL FOR LYMPHOMA RELAPSE DETECTION**

We have developed a score based on the dynamics and the combination of clinical and biological signs to alert the doctor of a possible recurrence of lymphoma

[figure not shown]
The considered clinical symptoms will be self-assessed (presence / absence or no problem / slight problem / medium problem / significant problem) by patients every 1 to 2 weeks, sent by their Smartphone or computer via the Internet, and will be analyzed by software that determines whether or not a relapse or significant complication is likely. The referring doctor will thus be alerted early and will summon the patient early for a check-up.

A similar application has been developed to detect relapse of lung cancer early (20, 21). The prospective study of this application showed interesting results in these patients with 100% sensitivity, 89% specificity, 81% PPV and 100% NPV with 11 symptoms studied. In the initial study to establish a detection algorithm based on only 6 symptoms, a NPV of 93% was already noted (20). In addition, relapses were detected on average 5 weeks before the scheduled date of the follow-up assessment (images every 3 months) (21).

An analysis of overall survival (monocentric and non-randomized) in our center also suggests a gain in survival of nearly 24% at 1 year ( $p = 0.02$ ) (22). This gain in survival is most likely related to the early initiation of salvage treatment and supportive care.

In the follow-up of the patients, it appeared that the algorithm was more sensitive if the patients were not very symptomatic at inclusion and had an initial score of less than 7 (by adding the scores of 0 to 3 for the symptoms concerning cough, dyspnea, pain, anorexia and asthenia: no problem = 0, mild problem = 1, medium problem = 2, significant problem = 3). A phase 3 study comparing this computerized surveillance with surveillance according to the usual method is in progress.

The results of the interim study suggest a favorable trend in overall survival in user and compliant patients (use at least once a week): 62% in the standard arm versus 87% in the SENTINEL arm:  $p(\text{logrank})=0,038$  (23).

Results of the interim analysis of the phase 3 study  
Per-protocol analysis of overall survival ( $p=0,038$ ).

## 1.4. DESCRIPTION AND JUSTIFICATION OF THE INTERVENTION UNDER STUDY

As part of this study, we want to assess the value of web-application monitoring of patients treated for lymphoma in complete or partial response.

The underlying assumption is that the use of new information and communication technologies can improve the clinical follow-up of patients. To date, access to the Internet and to portable technologies is sufficiently wide and democratized to consider the use of this type of telemonitoring in the field of health; in particular to facilitate the dissemination of information between the patient and the doctor. It is thus possible to imagine using this flow of information to generate alerts, in the particular case of the application with the doctor, for example according to the symptoms felt and informed by the patient.

Strengthening clinical monitoring in this indication in which routine imaging has not demonstrated its value, in particular through the implementation of remote monitoring completed by the patient, may present an advantage in terms of efficiency and earliness. support. In fact, in this pathology, up to 40% of patients relapse early (within 2 to 3 years), in the vast majority of cases symptomatically (less than 2% of asymptomatic relapses discovered by imaging); and finally, the current follow-up by tomodynamometry every 6 months, which generates costs and radiation exposures for a benefit considered rather low, has been carried out in symptomatic patients for several weeks.

In addition, reinforced clinical follow-up can improve the early detection of relapses, and would also aim to improve the monitoring of all the significant clinical complications frequent in patients suffering from a serious pathology (sepsis, thromboembolism, late iatrogenias, etc. ); if a survival benefit is to be hoped for, it will very probably be due on the one hand to the early detection of relapses and better control of the relapse through the implementation of early treatments, and on the other hand to the management and the early implementation of appropriate supportive care, if only through the management of depressive symptoms, or the management of iatrogenic or other complications.

However, in a context of increasing health needs and recourse to the health system, but also of medical shortage and strict control of health expenditure, strengthening the clinical monitoring of patients can only be considered by putting in place implement the means, if they prove to be effective, as efficient as possible, particularly in terms of time and costs. In this sense, involving the patient and implementing telemedicine solutions now appears very relevant by avoiding unnecessary travel and examinations.

## **1.5. BENEFITS ET RISKS**

### **1.5.1. Benefits**

#### **1.5.1.1. Individual benefits**

The expected benefit for patients using the Moovecare application will mainly be to have personalized follow-up, between 2 consultations. This strengthened clinical follow-up could allow earlier detection of a possible relapse or progression of lymphoma, promote early treatment and better control of the relapse. It could also improve the detection of possible complications related to treatment or the disease but also reduce the anxiety induced by routine surveillance examinations, and thus improve the quality of life of patients.

#### **1.5.1.2. Collective benefits**

Beyond the benefit for patients in terms of disease control and quality of life, the use of the Moovecare application makes it possible to space out the follow-up by imaging and thus reduce the stress and costs caused by the follow-up. standard of patients treated for lymphoma.

### **1.5.2. Risks**

#### **1.5.2.1. Individual risks**

##### **Constraints**

The constraints are minimal and consist in competing:

- for all patients, a quality of life questionnaire and a questionnaire relating to depression at inclusion and then at follow-ups at 3, 6, 9 and 12 months
- for patients in the “web app follow up” arm, a satisfaction survey during the 6-month follow-up and at least every 14 days the specific questionnaire via a computer or a smartphone. The entry time is of the order of 1 to 2 minutes.

There is no further examination.

##### **Risks associated with the disease**

The risks of natural progression of the disease were not affected by this study.

#### **1.5.2.2. Collective risks**

None

### **1.5.3. Benefit/risk balance**

As part of this study, we want to assess the value of web-application monitoring of patients treated for lymphoma in complete or partial response.

The web-application follow-up is a reinforced clinical follow-up with which it is unlikely that the events (complications or relapses) will be diagnosed later than during standard imaging follow-up. All

CONFIDENTIAL

patients will be followed in consultation every 3 months. It is therefore expected that the use of the Moovcare app will only benefit patients.

The underlying hypothesis is that a strengthening of clinical monitoring, where the patient can regularly inform his doctor about his symptoms, would allow earlier discovery of relapses, and / or any other event requiring medical treatment.

A web-application follow-up could thus promote the earlier treatment of relapses and / or other medical events occurring during follow-up, and thus improve the survival of patients and their quality of life as suggested by the phase study. III in bronchial cancer.

Optimizing clinical follow-up could also favor the spacing out of systematic imaging follow-up, which has limitations. This reduction in the frequency of check-ups would benefit the patient by reducing his exposure to radiation, but also the benefit of society by reducing the overall cost of monitoring patients treated for lymphoma.

## **2. OBJECTIVES END ENDPOINT**

### ***2.1. OBJECTIF ET CRITERE D'EVALUATION PRINCIPAL***

#### **2.1.1. Primary objective**

The main objective of the study is to show that follow-up via the Moovcare web-application could make it possible to better identify the significant complications occurring between two systematic follow-up consultations with the specialist in patients followed for high-risk lymphoma. relapse than with standard follow-up. The evaluation of the main objective will be carried out over 6 months of follow-up.

#### **2.1.2. Primary endpoint**

The primary endpoint is the appearance of a significant complication detected and confirmed by a medical consultation performed outside of standard follow-up.

The significant complications are:

- emergency hospitalization,
- a medical consultation without follow-up with medical prescription (imaging / drug prescription)
- a significant event at the classic follow-up consultation (very degraded PS, antibiotic therapy, supportive care with consultation, pulmonary embolism, sepsis, severe depression, etc.)

We will identify in the web-app group, the absence of alert in the event of complications and in the standard arm, the absence of medical consultation (attending physician) in the event of complications.

Complications diagnosed during the follow-up consultation will be reviewed in the form of a list by the coordinator, who will rule on the significance of the complication.

## **2.2. SECONDARY OBJECTIVES AND ENDPOINTS**

### **2.2.1. Secondary objectives**

The interest of web-application monitoring will also be assessed in terms of:

- progression-free survival,
- overall patient survival at 2 years,
- estimated time between the diagnosis of a complication, allowed by the application, and the theoretical date of the scheduled subsequent follow-up,
- proportion of hospitalization for life-threatening emergencies,
- total number of complications observed,
- quality of life of patients,
- the degree of patient compliance with the use of the web application
- the degree of satisfaction with the use of the web-application and the implementation of web-monitoring,
- number of significant complications whatever they may be (but defined above), which have arisen and not identified via the application (sensitivity calculation),
- number of significant complications whatever they may be (but defined above), which have arisen and identified in the systematic follow-up group, excluding systematic follow-up,
- Performance Status at relapse,
- description of health consumption in the 2 groups.

### **2.2.2. Secondary endpoints**

Progression-free survival is defined as the time between the date of the first examination making the diagnosis of partial response or complete response and the date of consultation allowing the diagnosis of the relapse.

The diagnosis of partial or complete response, as well as relapse in this study follows the definition of the Cheson criteria.

The time between the date of diagnosis of the relapse and the nearest consultation date scheduled as part of the standard follow-up will be evaluated. The same will be done with the date of diagnosis of significant complications.

The time taken to set up a treatment will also be evaluated. Thus, the time between the date of diagnosis of each event and the date of implementation of the care (1st psychological consultation, date of D1 of treatment, etc.) will be evaluated.

Overall survival is defined as the time between the date of diagnosis of the complete or partial response as defined in chapter 2.1.2 and death from any cause within 2 years.

Quality of life will be studied using the QLQ-C30 and HUMEUR PhQ9 questionnaires at inclusion and then follow-up consultations at 3, 6, 9 and 12 months.

Patient compliance with the use of the web application will be assessed based on the number of assessments completed by patients; an evaluation every 14 days is expected. Patients who have completed less than 1 assessment per 42 days (6 weeks) will be considered non-compliant. An overall compliance rate over the entire period and a rate per 14-day period can then be presented.

The satisfaction and feelings of patients with regard to the web-monitoring and the use of the web-application will be assessed by a self-questionnaire during the follow-up visit in the 6th month.

The calculation of the application's sensitivity is based on the evaluation of the number of alerts triggered by the application against the results of systematic or alert-triggered imaging examinations.

CONFIDENTIAL

The Performance Status will be assessed according to WHO recommendations.

The description of health consumption will be assessed by the number of consultations, imaging and laboratory tests performed by the patients in each group.

[figure not shown]

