### ***4.1. INCLUSION CRITERIA***

- 1) Patient with either:
  - a. T-cell lymphoma in first complete or partial response
  - b. Hodgkin lymphoma in 2nd complete or partial response including after autograft
  - c. c. Large B-cell diffuse lymphoma in 2nd complete or partial response including after autograft
- 2) End-of-treatment imaging in the last 4 weeks
- 3) Age  $\geq$  18 years
- 4) PS  $\leq$ 2 (WHO)
- 5) Patient with an initial symptoms score less than or equal to 5
- 6) Patient with internet access and mailbox
- 7) Patient affiliated to a social security scheme
- 8) Patient with written consent prior to any procedure specific to the study

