### ***4.2. NON INCLUSION CRITERIA***

- 1) Patient whose lymphoma progressed at the end of the specific treatment (evaluation <3 months after the end of the previous treatment)
- 2) Symptomatic brain or meninges localization
- 3) Presence or history of another cancer in the last 3 years, except skin cancers (other than melanoma), in situ cancers of the cervix or other cancers considered cured
- 4) Persons deprived of their liberty or under trusteeship
- 5) Dementia, mental impairment or psychiatric pathology that may compromise the informed consent of the patient and / or compliance with the protocol and follow-up of the study
- 6) Patients who cannot follow the protocol for psychological, social, family or geographical reasons,
- 7) Pregnancy or breast-feeding
- 8) Patient participating in another interventional study

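### PFS and OS are timed from the diagnosis of response instead of randomisation, which counts guaranteed event-free time and closes the 2-year OS window before M24

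*Combined protocol and SAP*

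**What the plan says.** Section 2.2.2 gives the PFS definition: "Progression-free survival is defined as the time between the date of the first examination making the diagnosis of partial response or complete response". The interval closes, on that definition, at "the date of consultation allowing the diagnosis of the relapse". For OS it says: "Overall survival is defined as the time between the date of diagnosis of the complete or partial response as defined in chapter 2.1.2", and it counts "death from any cause within 2 years". The matching objective in 2.2.1 is "overall patient survival at 2 years".

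The follow-up under test uses another clock. Section 5.1.2 ties the start of surveillance to inclusion. The schedule in 5.3 runs from baseline to M24, and 5.6.3 and 7.3 give each included patient 24 months of follow-up.

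Entry requires an existing response (4.1), which may be a second response after autograft, together with "End-of-treatment imaging in the last 4 weeks". Section 4.2 excludes a "Patient whose lymphoma progressed at the end of the specific treatment". Section 6.2.1 plans Kaplan-Meier curves and a Cox model and says nothing about delayed entry.

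**The concern.** The question for PFS and OS is what happens to patients after they are assigned to web or standard follow-up. A clock that starts at response adds a stretch before assignment in which neither event can occur: a patient who died or lost the response in that stretch would not be in the trial. Kaplan-Meier without delayed entry treats the stretch as time at risk, so the curves stay flat at the start and sit too high afterwards.

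The OS window has a related fault. Two years from response ends before 24 months from inclusion whenever response precedes inclusion. Deaths between those two dates are observed under the visit schedule but fall outside the definition. The protocol names survival as a hoped-for benefit (1.4, 1.5.3), and PFS and OS head its list of secondary objectives, so the quoted rates will be read.

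**Working it through.** **Plan's own figure.** The plan gives no design figure for PFS or OS. Its maximum of 40 patients per group comes from the primary endpoint alone. A two-look triangular test of 90% against 60%, with 5% read as two-sided and 90% power, has log odds ratio ln 6 = 1.792 and maximum information 3.65. That gives 4 × 3.65 / (0.75 × 0.25) ≈ 78 in total, close to the planned 80. Nothing below changes it.

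**Step 1: the two clocks.** Inclusion and randomisation are taken as the same day.

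| | Starts | Ends |
|---|---|---|
| PFS (2.2.2) | first examination showing response | relapse consultation |
| OS (2.2.2) | diagnosis of response | death within 2 years |
| Follow-up (5.1.2, 5.3, 5.6.3, 7.3) | inclusion | M24 |

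**Step 2: response dated at the end-of-treatment imaging.** The gap is 0 to 28 days. At 28 days:

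- The OS window closes 730.5 − 28 = 702.5 days after inclusion; 702.5 / 30.4375 = month 23.1.
- The lead-in is 28 / 730.5 = 3.8% of the window.

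To size the effect, take the relapse range in section 1.1 (20% to 40% within 2 or 3 years) and assume a constant hazard. For a proportion r relapsing by y years, λ = −ln(1 − r)/y. The 2-year event-free rate is exp(−2λ) from inclusion and exp(−λ × 702.5/365.25) on the response clock.

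| Relapse | From inclusion | Response clock | Excess (points) |
|---|---|---|---|
| 20% by 3 years | 86.2% | 86.7% | 0.5 |
| 20% by 2 years | 80.0% | 80.7% | 0.7 |
| 40% by 3 years | 71.1% | 72.1% | 0.9 |
| 40% by 2 years | 60.0% | 61.2% | 1.2 |

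(Excesses are from unrounded rates.)

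**Step 3: response shown earlier, OS.** The documents give neither mortality nor the length of a longer gap, so both are assumed: 24-month mortality m of 20% to 40%, and a gap d of 1, 3 or 5 months for every patient. With h = −ln(1 − m)/24, the 2-year rate on the response clock is exp(−h(24 − d)), against 1 − m from inclusion.

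| Gap d | Window closes | m = 20% (80%) | m = 30% (70%) | m = 40% (60%) |
|---|---|---|---|---|
| 1 month | month 23 | 80.7% (+0.7) | 71.0% (+1.0) | 61.3% (+1.3) |
| 3 months | month 21 | 82.3% (+2.3) | 73.2% (+3.2) | 64.0% (+4.0) |
| 5 months | month 19 | 83.8% (+3.8) | 75.4% (+5.4) | 66.7% (+6.7) |

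The share of deaths by M24 that goes uncounted is the excess divided by m: about 3% to 4% at 1 month, 10% to 11% at 3 months and 17% to 19% at 5 months.

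**Step 4: the comparison between arms.** The gap is fixed before allocation, so its expected length is the same in both arms. If chance made the mean gap differ by one month, at 30% mortality the 2-year rates would move apart by about (75.4 − 73.2)/2 = 1.1 points. The standard error of a 70% rate in 40 patients is √(0.7 × 0.3/40) ≈ 7 points, and of the difference between arms about 7 × √2 ≈ 10 points.

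**The case against.** The strongest reply is that the gap may be short. The end-of-treatment scan, at most 4 weeks old, may well be the examination that establishes the qualifying response, and the effect is then about 1 point. The longer gaps are assumptions applied to every patient, although 4.1 also admits T-cell lymphoma in first response and second responders without autograft. The word *first* appears only in the PFS definition, so an early response date is less plausible for OS. This all stands, and it limits the size. It does not remove the mismatch between the clocks.

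Three stronger readings are tempting but not supported:

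- A reader might infer that the clock must start at a pre-transplant response. The text permits this, most plausibly for PFS, but no section says so or gives the delay.
- A reader might infer that the choice of origin favours one arm. Response is dated before 1:1 randomisation, and 6.2.3 minimises on autologous transplant, relapse and lymphoma type, which are likely drivers of a long gap. Chance imbalance remains possible but is small against sampling error.
- A reader might infer that response is left undefined, because 2.1.2 covers only significant complications. Section 2.2.2 itself says that response and relapse follow the Cheson criteria, so the fault is a wrong cross-reference.

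It is also fair that moving time zero is not the only cure: keeping the response origin with delayed entry at randomisation would also remove the guaranteed event-free time.

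**Conclusion.** The point holds as a misalignment of time zero that inflates the absolute 2-year PFS and OS estimates in both arms and leaves some observed deaths outside the OS definition. For OS these are one effect seen from two sides, not two harms: the uncounted share times mortality equals the overstatement.

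With the response dated at the end-of-treatment imaging, the overstatement is about 1 point (0.5 to 1.3) and the OS window closes at about month 23. With an assumed gap of 3 to 5 months for every patient, it is about 2 to 7 points for OS. The top of that range needs both 40% mortality and a 5-month gap throughout. All the sizes rest on a constant hazard, and the longer gaps and the mortality range are not in the documents.

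There is no systematic bias between arms. Both endpoints are secondary, and the sample size and the 6-month primary analysis are unaffected.

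**What to change.** In 2.2.2, define PFS and OS from the date of randomisation, with the 2-year OS window running to 24 months after randomisation (M24). Replace the reference to 2.1.2 with the Cheson criteria already named in 2.2.2. If time from response is also of interest, report it as a supplementary analysis with delayed entry at randomisation.

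The cost is a change of wording. Randomisation is performed in the e-CRF (6.2.3), so its date should already be on record, and no patients or visits are added. The downside is that the quoted survival rates become slightly less favourable.

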## **5.6. RULES FOR SUBJECT WITHDRAWAL**

### **5.6.1. Criteria for a study subject's early withdrawal**

Patients can withdraw their consent and request to withdraw from the trial at any time and for any reason, without losing the right to be treated by their doctor. The investigator may also prematurely discontinue a patient's participation in the trial for any reason that would serve the best interests of the patient, including the case of an intercurrent disease or an adverse event. In the event of premature discharge, at any time and for any reason, the investigator should notify the patient, if necessary, and document the reasons as fully as possible.

Test exits must be reported in particular for the following possible reasons:

- Death,
- Withdrawal of consent with the patient's request not to use the data already collected,
- Wrongly included,
- Choice of investigator,
- Patient choice,
- No seizure in the application for 6 consecutive weeks apart from a pathology or relapse preventing seizure,
- Lost view.

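### Progression-free survival ends only at diagnosed relapse and has no rule for death, and no between-arm comparison is stated for PFS, OS, QLQ-C30 or PHQ-9

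*Combined protocol and SAP*

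**What the plan says.** Section 2.2.1 opens its list of secondary objectives with "The interest of web-application monitoring will also be assessed in terms of" and includes progression-free survival, overall survival at 2 years and quality of life.

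Section 2.2.2 runs PFS from the first examination showing partial or complete response to "the date of consultation allowing the diagnosis of the relapse". Death is not named as an event, and there is no censoring or competing-risk rule for it. In the same section OS ends at "death from any cause within 2 years". OS starts at "the date of diagnosis of the complete or partial response as defined in chapter 2.1.2", but section 2.1.2 defines complications, not response. This is a harmless slip, because section 2.2.2 itself names the Cheson criteria.

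The planned statistical methods in section 6.2 give Kaplan-Meier curves with medians and 95% confidence intervals. They add a multivariate Cox model, with no covariates named, whose output is called odds ratios. QLQ-C30 is compared with inclusion and then analysed in a repeated-measures mixed model whose terms are not listed. PHQ-9 is described and compared with inclusion, with no model. The sample size section sets 1:1 randomisation and an explicit between-group hypothesis, for the primary endpoint only. Among the secondary endpoints, health consumption is explicitly described in each group.

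**The concern.** PFS normally counts death as an event. Leaving it out matters here because of the trial's own rationale. Section 1.4 hopes that any survival benefit would come partly from the app's ability to "improve the monitoring of all the significant clinical complications frequent in patients suffering from a serious pathology (sepsis, thromboembolism" and others in its list). Such complications can kill without relapse, and a relapse-only endpoint does not register those deaths. Because no rule is given, one analyst could censor them and another could keep the patients event-free to month 24. Both would be following the protocol, with different answers.

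On the second part, section 1.5.3 says web follow-up could promote earlier treatment and "thus improve the survival of patients and their quality of life". Change from inclusion cannot separate an app effect from recovery after treatment that both arms share. Only the randomised contrast can, and with several secondary endpoints in a small trial its form should be fixed before the data are seen.

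**Working it through.** **Plan's own figure.** The plan gives no event count or power for these endpoints. The only sizing figure is a maximum of 40 per group for the primary endpoint (90% against 60%, alpha 5%, power 90%). The two-sided pooled formula gives [1.960·√(2·0.75·0.25) + 1.282·√(0.9·0.1 + 0.6·0.4)]² / 0.30² = 41.7, so 42 per group. An approximate two-look triangular test gives a maximum of about 39. The stated 40 is consistent, so I use 80 patients as the maximum and 40 as the number at the first analysis (2x20).

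**Assumptions.**
- r = relapse by 24 months, 20-40%. Section 1.1 gives this range for 2 or 3 years in lymphoma generally. This population is at high risk, so 50-60% is shown as well.
- d = death without relapse by 24 months, 5-10%. The documents give no figure.
- Constant, independent hazards, no other loss, and a hazard ratio of 0.5.

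**Formulas.**
- True PFS = (1−r)(1−d).
- Gap if deaths are censored = (1−r) − PFS = (1−r)·d.
- Gap if deaths are kept event-free = share of patients who die first = λd/(λr+λd) × (1−PFS), with λr = −ln(1−r) and λd = −ln(1−d).
- Deaths not counted = 80 × that share.
- PFS events D = N(1−PFS).
- Power = Φ(√(D/4)·ln 2 − 1.96), two-sided 5%.

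**Example, r = 0.20, d = 0.10.** PFS = 0.80 × 0.90 = 0.72. Censored gap = 0.80 × 0.10 = 0.08. λr = 0.223 and λd = 0.105, so the event-free gap = 0.105/0.329 × 0.28 = 0.090, or 7.2 of 80 patients. D = 80 × 0.28 = 22.4, and power = Φ(√5.6 × 0.693 − 1.96) = 0.375.

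| r | d | PFS | Gap, censored | Gap, event-free | Deaths not counted (of 80) | D, N=80 | Power, N=80 | Power, N=40 |
|---|---|---|---|---|---|---|---|---|
| 0.20 | 0.05 | 0.760 | 0.040 | 0.045 | 3.6 | 19.2 | 0.33 | 0.19 |
| 0.20 | 0.10 | 0.720 | 0.080 | 0.090 | 7.2 | 22.4 | 0.38 | 0.21 |
| 0.30 | 0.05 | 0.665 | 0.035 | 0.042 | 3.4 | 26.8 | 0.43 | 0.25 |
| 0.30 | 0.10 | 0.630 | 0.070 | 0.084 | 6.7 | 29.6 | 0.47 | 0.27 |
| 0.40 | 0.05 | 0.570 | 0.030 | 0.039 | 3.1 | 34.4 | 0.53 | 0.30 |
| 0.40 | 0.10 | 0.540 | 0.060 | 0.079 | 6.3 | 36.8 | 0.56 | 0.32 |

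With r = 0.50-0.60 the gaps are 2-5 points (censored) and 3-7 points (event-free), about 3-6 deaths are not counted, and power with 80 patients is 61-70%.

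**Precision.** The 95% interval for the hazard ratio runs a factor exp(2·1.96/√D) either side. With 80 patients and r = 0.20-0.40 this is 2.45 at D = 19.2 and 1.91 at D = 36.8.

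**Median.** At r = 0.20-0.40 overall PFS at 24 months is 54-76%, so the overall median is not reached. At r = 0.50-0.60 it is 36-47.5%, so it is reached. A 24-month estimate is informative either way, and section 2.2.1 asks for survival at 2 years.

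**Follow-up for death and relapse.** Section 5.6.1 says "Test exits must be reported in particular for the following possible reasons". The list includes death, but also six consecutive weeks without an app entry, which can apply only to the web arm. Section 5.6.2 returns patients who exit to usual care, while section 7.3 says all are followed for 24 months. If exit ends data collection, censoring at last contact may differ by arm.

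**The case against.** The strongest reply to the first part is that the deaths are not lost: OS counts them, and relapse detection is one of the aims in section 3.1. That stands, and it is why renaming the endpoint is as sound a remedy as adding death. It does not rescue the current text, which carries the PFS label and leaves death without a rule.

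On the second part, a reader might infer that only pooled results are planned, because section 6.2 says the criteria will be presented globally. The documents do not support that. The sentence lacks a full stop and may be cut short, and it also covers the primary endpoint, which is plainly compared between arms. The Cox and mixed models could carry arm. Section 1.3 reports the lung-cancer trial by arm ("62% in the standard arm versus 87% in the SENTINEL arm"), so an arm comparison is probably intended here too. What remains is that none is stated.

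Three other inferences go too far. Starting both clocks before randomisation does not by itself bias the comparison, since the rule is the same in both arms. PS at relapse and time to treatment are not further randomised contrasts left unstated: they exist only in patients with an event. Nor is the median the only survival result named, since curves and Cox ratios are named too.

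Finally, these are secondary endpoints with low power. That is true, and it calls for an exploratory label; it does not justify leaving the contrast open.

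**Conclusion.** The point holds in two parts. First, the endpoint labelled PFS is time to relapse detection, and no other section repairs the definition. At 20-40% relapse and 5-10% death without relapse it overstates 24-month PFS by 3-8 points (deaths censored) or 4-9 points (deaths event-free), leaving about 3-7 deaths among 80 patients outside the endpoint. These sizes rest on assumed rates. The definitional gap does not.

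Second, no between-arm comparison is stated for PFS, OS, QLQ-C30 or PHQ-9, and inclusion is the only comparator named for the questionnaires. This is an omission in specification, not evidence of a pooled-only analysis.

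The primary endpoint is unaffected. Even when corrected, the PFS comparison is exploratory: 33-56% power at a hazard ratio of 0.5 is the case with all 80 patients, and it falls to 19-32% at 40. It is also descriptive, because section 5.3 schedules imaging every 6 months in the standard arm and only on an alert or clinical sign in the web arm, so relapse is ascertained differently. The change is worth making before analysis.

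**What to change.** - **PFS.** Either count death from any cause as an event, or rename the endpoint time to relapse and treat death as a competing event.
- **Survival by arm.** For PFS and OS give Kaplan-Meier curves by randomised arm with 24-month estimates, and the Cox hazard ratio for arm with its 95% confidence interval. Replace the term odds ratios. If time to relapse is chosen, give cumulative incidence by arm in place of the Kaplan-Meier curve.
- **Questionnaires.** Specify repeated-measures mixed models for QLQ-C30 and, newly, PHQ-9, with arm, time, arm-by-time and baseline score, and report between-arm differences with 95% confidence intervals.
- **Labels.** Call these analyses exploratory. State that relapse is ascertained differently by arm, and that PS at relapse and time to treatment are descriptive by arm.
- **Follow-up.** Reconcile sections 5.6.1 and 5.6.2 with section 7.3, so that death and relapse are recorded to month 24 in both arms, including after an exit for missing app entries.
- **Optional.** Start both times at randomisation and correct the cross-reference to section 2.1.2.

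The cost is analysis-plan wording, a few more outputs and a slightly less favourable PFS figure. Arm and the questionnaires are already collected. Complete follow-up after exit may need some effort, depending on how those sections are reconciled. The low power and the arm-dependent detection of relapse remain and can only be stated.
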